1    **Official Title**

2    **Influenza Vaccination Effectiveness of a Quadrivalent Inactivated Vaccine in**  
3    **Pregnant Women and Young Infants (Aged 6 months and Below) During**  
4    **Influenza Season 2019-2020**

5

6    **Unique Protocol ID: 16708**

7    **6 May 2021**

8

9

10

11

12

13

14

15

16

17

18

19

20 **Statistical analysis**

21 Women were excluded from the statistical analysis for the following reasons that  
22 occurred before the onset of influenza season: decision to withdraw from the study,  
23 loss to follow-up, post-partum influenza vaccination (cocooning), pregnancy  
24 discontinuation, spontaneous abortion, perinatal death. Women were followed for the  
25 entire influenza season, regardless of onset of influenza or ILI. The analysis was  
26 restricted to the influenza season. The primary outcome of the study was influenza  
27 onset in pregnant women. Secondary outcomes were the onset of influenza in their  
28 infants and the onset of ILI, ARI, febrile episode, pneumonia, healthcare seeking,  
29 hospitalization, use antibiotics and use of antivirals in pregnant women and their  
30 infants. Categorical and continuous variables were compared between vaccinated and  
31 unvaccinated groups using the  $\chi^2$  test and T-test, respectively. Logistic regression  
32 analysis was conducted in order to identify factors significantly associated with a  
33 history of influenza vaccination in 2019-2020. Odds ratio (OR) and confidence  
34 intervals (CIs) were estimated. We have used a Bayesian model selection for logistic  
35 regression models with random intercept. The primary outcome of interest was to  
36 estimate the average rate of influenza for each group (vaccinated versus unvaccinated  
37 group). Our data was a 2 by 2 cross-tabulated data arising from two binary variables  
38 with possible values 0 or 1. The first variable was whether a pregnant woman has  
39 been vaccinated (value =1) or not (value =0). The second variable was the age group  
40 of the pregnant woman. The first group consisted of pregnant women aged less than  
41 32 years (value =0) or not (value=1). We compared the vaccinated pregnant women  
42 group with the group of non-vaccinated pregnant women to model the proportion of  
43 effectiveness that is the event that a pregnant woman had influenza. We used the  
44 Bayesian beta-binomial model due to data heterogeneity because of a large number of

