45 zeros were observed. Given this heterogeneity assumption, a Bayesian hierarchical  
46 random-effects model was used to analyze the data. The assumption of our model  
47 was that the number of individuals  $y_j$  responding to influenza vaccination is  
48 binomially distributed as:

49  $y_j \sim \text{Binomial}(p_j, n_j)$ ,

50 where the success rate ( $p_j$ ) was the probability of influenza onset in mothers and  $n_j$   
51 was the number of individuals in the  $j$ th group. We note that there are only 2 groups  
52 ( $j=1,2$ ): the vaccinated and the not vaccinated groups. The probability ( $p_j$ ) itself  
53 follows a beta distribution with parameters ( $a_j, b_j$ ). Non-informative distributions  
54 priors distributions were placed on the parameters of the beta distributions. P-values  
55 of 0.05 or less were considered statistically significant. IVE against influenza was  
56 estimated as follows:  $[1 - (\text{incidence rate of influenza in vaccinated women} / \text{incidence rate of influenza in unvaccinated women})] \times 100$  [11]. The statistical analysis was  
57 conducted using R 3.6 (R Foundation for Statistical Computing).  
58

59

60

61 **Results**

62 A total of 949 pregnant women were enrolled in the study (Figure 1). Of them, 94  
63 women were excluded from the analysis because of the following reasons: lost to  
64 follow-up or decision to withdraw from the study (65 women), post-partum influenza  
65 vaccination (cocooning) (25 women), spontaneous abortion (3 women), and perinatal  
66 death (1 woman). Therefore, 855 pregnant women were included in the analysis.  
67 Their mean age was 32.9 years (range: 18-45 years) and their mean gestational age at  
68 enrollment was 23.3 weeks (range: 3-39 weeks).

69 Of the 855 pregnant women, 525 (61.4%) were vaccinated against influenza and 330  
70 (38.6%) refused vaccination. No serious adverse event occurred. Pregnant women  
71 with a history of influenza vaccination the past (2018-2019) season were more likely  
72 to get vaccinated against influenza in 2019-2020 compared to women with no history  
73 of vaccination (91.8% versus 55.1%, p-value<0.001). In the logistic regression  
74 analysis the following variables were significantly associated with a history of  
75 influenza vaccination in 2019-2020: lower gestational age (OR: 0.998; CI: 0.998-  
76 0.999), influenza vaccination the past season (OR: 8.8; CI: 4.7-16.2), and no smoking  

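### The post-partum vaccination exclusion is also applied to the vaccinated share and to the regression of factors for vaccination, where it selects 25 women on the outcome being described

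*SAP*

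**What the plan says.** The SAP's Statistical analysis section opens with a single list of reasons for leaving women out. It covers the statistical analysis as a whole and is limited only by timing: the reasons are those that "occurred before the onset of influenza season: decision to withdraw from the study", followed by loss to follow-up, post-partum vaccination (cocooning) and pregnancy loss. The same section plans a logistic regression: "analysis was conducted in order to identify factors significantly associated with a" history of influenza vaccination in 2019-2020. No separate analysis set is given for that regression.

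The first part of the Results gives the counts. "A total of 949 pregnant women were enrolled in the study (Figure 1). Of them, 94" were excluded, made up of "follow-up or decision to withdraw from the study (65 women), post-partum influenza" "vaccination (cocooning) (25 women), spontaneous abortion (3 women), and perinatal" "death (1 woman). Therefore, 855 pregnant women were included in the analysis". The vaccinated share follows: "Of the 855 pregnant women, 525 (61.4%) were vaccinated against influenza and 330" (38.6%) are described as having declined vaccination. The comparison by past-season vaccination (91.8% versus 55.1%) and the regression results come directly after this, with no new denominator. The odds ratio for past-season vaccination is 8.8 (CI 4.7-16.2).

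The SAP does not give the vaccination status of the 69 women excluded for other reasons. It does not place the exclusions before or after the vaccination decision. It does not say whether vaccination in 2019-2020 means vaccination in pregnancy only.

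**The concern.** Excluding women vaccinated after delivery makes sense when influenza incidence is compared by vaccination status in pregnancy, because later vaccination contaminates the unvaccinated group. It has no such purpose when vaccination is itself the outcome. Describing who was vaccinated in pregnancy, and which factors go with it, needs no follow-up through the influenza season.

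In that analysis the cocooning rule does harm. A woman can meet it only by being vaccinated post-partum, which in ordinary usage means that she was not vaccinated in pregnancy. The rule can then remove women from one outcome category only. At stake are the reported vaccinated share and the odds ratios for past-season vaccination, smoking and gestational age. The past-season odds ratio is the most exposed that can be examined, because it rests on a small cell: few women vaccinated the season before went unvaccinated in 2019-2020.

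**Working it through.** **Inputs (SAP, Results, first part).** Enrolled 949. Excluded: 65 lost or withdrawn, 25 cocooning, 3 spontaneous abortion, 1 perinatal death. Vaccinated 525 and unvaccinated 330 of those analysed. Share vaccinated by past-season status: 91.8% versus 55.1%.

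**1. The SAP's own figures.** 65 + 25 + 3 + 1 = 94; 949 − 94 = 855; 525/855 = 61.4%; 330/855 = 38.6%. All reproduce.

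**2. The 25 restored as unvaccinated in pregnancy.**
- Unvaccinated: 330 + 25 = 355. Share dropped by the rule: 25/355 = 7.0%.
- Uptake in pregnancy: 525/(855 + 25) = 525/880 = 59.7%, which is 1.7 points below 61.4%.

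**3. The other reading of the outcome.** If any vaccination in 2019-2020 counts, the 25 are vaccinated: (525 + 25)/880 = 550/880 = 62.5%.

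**4. All 949 enrolled.** The other 94 − 25 = 69 women have unknown status.
- None of the 69 vaccinated: 525/949 = 55.3%.
- All 69 vaccinated: 594/949 = 62.6%.
- Break-even with 61.4%: (525/855) × 949 − 525 = 57.7. So 58 or more of the 69 (58/69 = 84%) would have to be vaccinated for 61.4% not to exceed the share over all 949.

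**5. Past-season odds ratio.** The percentages alone give a crude value of (91.8/8.2)/(55.1/44.9) = 9.1. If all 855 women have past-season status recorded, two integer tables fit: 135/147 with 390/708, and 134/146 with 391/709. Using the first, the cells are 135 vaccinated and 12 unvaccinated (past season yes), and 390 and 318 (past season no). The crude odds ratio is 135 × 318/(12 × 390) = 9.2.

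If k of the 25 had past-season vaccination, it becomes 135 × (318 + 25 − k)/[(12 + k) × 390]:

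| k | Basis | Crude OR |
|---|---|---|
| 0 | none | 9.9 |
| 1 | near the share in the other unvaccinated women, 12/330 = 3.6% | 9.1 |
| 4 | near the cohort share, 147/855 = 17.2% | 7.3 |
| 25 | extreme bound | 3.0 |

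The second table gives 9.1 at the start, 9.8 for k = 0 and 7.3 for k = 4.

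**Limit of step 5.** The rebuilt table is illustrative. It puts 12 women in the past-season-yes, unvaccinated cell among 855, whereas Table 1 lists 14 such women in the subset of 636. So either some past-season data are missing or the reported figures do not agree. One table with 14 in that cell that matches both percentages is 157/171 and 368/668, which assumes 16 women with missing status (855 − 171 − 668). It gives 157 × 300/(14 × 368) = 9.1 at the start, 157 × 325/(14 × 368) = 9.9 for k = 0 and 157 × 321/(18 × 368) = 7.6 for k = 4, so the picture is much the same.

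Nothing comparable can be computed for smoking or gestational age, because the counts by vaccination status in the 855 are not given.

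**The case against.** The strongest reply is that nothing is mislabelled. The 61.4% is stated as a share of the 855, and all exclusion counts stand just above it, so a reader can recompute it. Uptake is neither the primary nor a listed secondary outcome. This stands, and it limits the weight of the point. It does not answer the regression, which is a stated analysis in which the cocooning rule acts on the dependent variable.

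A second reply is that the literal outcome is vaccination in 2019-2020, under which the 25 are vaccinated and the share would be 62.5%. This also stands as a possible reading. It changes the direction of the shift but not the conclusion: on either reading the 25 belong in the denominator.

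Third, no changed conclusion is shown. In the plausible cases the crude odds ratio stays between about 7.3 and 9.9, inside the reported interval of 4.7-16.2, and even the extreme case points the same way. That is correct. It is also correct that the use of all 855 in the regression is inferred from the order of the text. No number is given for the model, and the smoking counts in Table 1 (376 of 406 and 206 of 230) show missing data, so a complete-case model would be smaller.

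A reader might go further and infer three things that the document does not support:
- **Uptake is overstated by at least the 25.** The range over all 949 reaches 62.6%, above 61.4%.
- **All 94 exclusions followed the vaccination decision.** The SAP places them only before the season, and some of the 65 lost or withdrawn women may have left before any decision.
- **The 25 were the less firm refusers.** No reason for post-partum vaccination is given. Enrolment ran to 39 weeks, so delivery before vaccination is equally possible.

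**Conclusion.** The point holds as a modest one. The cocooning exclusion does not belong in the description of vaccination in pregnancy or in the regression of its predictors. It selects on the outcome of that regression and drops 7.0% of the women known to be unvaccinated in pregnancy. For uptake in pregnancy among the 880 women whose status can be placed, the figure moves from 61.4% to 59.7%. The odds ratios would change by an amount that the document does not allow to be fixed. For past-season vaccination, plausible crude values run from about 7.3 to 9.9.

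This rests on two assumptions: that cocooning means not vaccinated in pregnancy, which the SAP implies but does not spell out, and that the regression was run on the 855 or on those of them with complete data. The direction of any bias over all 949 enrolled women is not established. The primary influenza vaccine effectiveness (IVE) analysis is not affected.

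**What to change.** State in the Statistical analysis section that the post-partum vaccination exclusion applies only to the effectiveness and morbidity analyses. Define the regression outcome as vaccination during pregnancy. Rerun the vaccinated share and the regression with the 25 women counted as unvaccinated in pregnancy, and give the number of women in the model. Report the vaccination status of the other 69 excluded women where it is known; otherwise give the 55.3% to 62.6% range beside the main figure.

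The cost is about one sentence of text, a small rerun and a slightly less favourable uptake figure. The rerun needs covariate records for the 25, and the document does not say how complete these are. For women who withdrew or were lost, status may be unobtainable, which is why the range is offered as the fallback.

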159	Healthcare seeking	5 (1.2)	5 (2.2)	0.359
160	Hospitalization	0 (0.0)	1 (0.4)	0.184
161	Use of antibiotics	11 (2.7)	7 (3.0)	0.807
162	Use of antivirals	3 (0.7)	4 (1.7)	0.245

163

164 \* laboratory-confirmed influenza

165 ARI: acute respiratory infection; ILI: influenza-like illness

166

167

168

169

170 **Table 3. Morbidity (%) of infants (n=474) by maternal influenza vaccination status**

171	Type of morbidity	Vaccinated	Unvaccinated	P-value
172		n = 281 (%)	n = 193 (%)	
173	Influenza*	4 (1.4)	4 (2.1)	0.59
174	Febrile episode	7 (2.5)	8 (4.1)	0.312
175	ARI	17 (6.0)	27 (14.0)	0.012
176	ILI	6 (2.1)	6 (3.1)	0.507
177	AOM	1 (0.3)	2 (1.0)	0.358
178	Pneumonia	0 (0.0)	1 (0.5)	0.227
179	Healthcare seeking	6 (2.1)	10 (5.2)	0.144
180	Hospitalization	0 (0.0)	1 (0.5)	0.277
181	Use of antibiotics	4 (1.4)	5 (2.6)	0.360
182	Use of antivirals	0 (0.0)	3 (1.6)	0.036

183

184 \* laboratory-confirmed influenza

185 ARI: acute respiratory infection; ILI: influenza-like illness; AOM: acute otitis media

186

187

188

189

190

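### The unqualified statement that there were no serious adverse events follows a count from which four pregnancy losses of unstated vaccination status had been removed, so it is either in conflict with the document's own events or unsupported

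*SAP*

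**What the plan says.** The exclusion rule in the SAP's Statistical analysis section removes women for listed reasons that arose before the influenza season. Three of these are pregnancy outcomes: "discontinuation, spontaneous abortion, perinatal death. Women were followed for the" is the line that carries them.

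The Results section opens with "A total of 949 pregnant women were enrolled in the study" and then accounts for 94 exclusions. The list includes "vaccination (cocooning) (25 women), spontaneous abortion (3 women), and perinatal", and continues with "death (1 woman). Therefore, 855 pregnant women were included in the analysis". The 855 are split into 525 vaccinated women and 330 who refused. The next sentence is "No serious adverse event occurred". It does not say whether it covers all participants or only vaccinated women, over what period, or whether a judgement of causality was involved. The vaccination status of the four women with losses is not given.

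Tables 2 and 3 each have a hospitalization row, with the vaccinated column first:

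- Women: "Hospitalization 0 (0.0) 1 (0.4) 0.184"
- Infants: "Hospitalization 0 (0.0) 1 (0.5) 0.277"

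**The concern.** Removing women whose pregnancy ended before the season is a defensible choice for an influenza endpoint counted during the season. It is not a neutral choice for a safety statement, because it takes out the pregnancy outcomes that matter most when a vaccine is given in pregnancy. The safety sentence stands directly after the reduced count and carries no qualifier. A reader would take from it that no serious event happened in the study, although the same document reports a perinatal death, three spontaneous abortions and two hospitalizations. What is at stake is the safety conclusion only, but in a study of vaccination in pregnancy that conclusion will be cited.

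**Working it through.** **Inputs (all from the SAP).** Results: 949 enrolled; exclusions of 65 (lost or withdrawn), 25 (post-partum vaccination), 3 (spontaneous abortion) and 1 (perinatal death); 525 vaccinated and 330 unvaccinated. Tables 2 and 3: hospitalizations 0/406 v 1/230 in women and 0/281 v 1/193 in infants, by maternal vaccination.

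**1. Reproduce the plan's count.** 65 + 25 + 3 + 1 = 94; 949 − 94 = 855; 525 + 330 = 855. The figures agree exactly, which confirms that the four losses are outside the 855.

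**2. Reproduce the hospitalization rows.** Uncorrected chi-square gives p = 0.184 for women, as printed. For infants it gives p = 0.227, where Table 3 prints 0.277. The pneumonia row of Table 3 has the same 0 v 1 counts and prints 0.227, so 0.277 is probably a transposed digit. The 0 v 1 split is not affected.

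**3. Read the sentence for all participants.** Events in the document that it would have to account for: 3 + 1 + 1 + 1 = 6 (three spontaneous abortions, one perinatal death, one hospitalized woman, one hospitalized infant). The four losses among the enrolled women are 4/949 = 0.42% (Clopper-Pearson 95% CI 0.11% to 1.08%). On any ordinary meaning of serious, a perinatal death and two hospitalizations do not fit with a claim of none.

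**4. Read the sentence for vaccinated women only.** Both hospitalizations drop out, since both are in unvaccinated groups. The four losses remain open. If k of them were in vaccinated women, and only the losses are added back to the 855, the proportions are k/(525 + k) in vaccinated women and (4 − k)/(330 + 4 − k) in unvaccinated women:

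| k | Vaccinated | Unvaccinated |
|---|---|---|
| 0 | 0/525 = 0% | 4/334 = 1.20% |
| 1 | 1/526 = 0.19% | 3/333 = 0.90% |
| 2 | 2/527 = 0.38% | 2/332 = 0.60% |
| 3 | 3/528 = 0.57% | 1/331 = 0.30% |
| 4 | 4/529 = 0.76% | 0/330 = 0% |

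The exact 95% upper limit for 0/525 is 0.70%; the interval for 4/529 is 0.21% to 1.92%. The document does not favour any row over another.

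**5. Allow for the 65 lost or withdrawn women.** Their vaccination status is not given either. If all 65 were vaccinated, the denominator at k = 4 becomes 525 + 4 + 65 = 594, and 4/594 = 0.67%. So at k = 4 the figure lies between 0.67% and 0.76%. Any pregnancy losses among these 65 women that the study did not learn of are not in the count.

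**The case against.** The strongest reply is that the sentence follows the vaccinated/refused split, so its natural meaning is events after vaccination. That reading needs no judgement of causality, and both hospitalizations are then consistent with the sentence. One of them is in any case an infant, not one of the 855 women, and Tables 2 and 3 already compare hospitalizations by group. It can be added that the exclusion rule is written for the statistical analysis, whose listed outcomes are influenza, morbidity and healthcare use. Nothing but the position of the sentence shows that safety was judged on the reduced set. Definition and attribution of serious events are commonly left to a protocol, and this is an effectiveness study.

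Most of that stands, and it limits the point. A reader might infer that the document contradicts itself outright. That is shown only if the sentence covers all participants. A reader might also infer that the exclusion rule makes the claim true by construction. It does not: the rule removes only listed reasons that arose before the season, so later losses and other serious events could still occur among the 855, and a maternal hospitalization is in fact recorded. The lack of a definition in this document is not counted as a fault here.

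The reply does not rescue the sentence. On the after-vaccination reading it still needs to be known that none of the four losses followed vaccination, and the document does not say so. A reading restricted to vaccine-related events would need a causality assessment that the document does not mention.

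**Conclusion.** The concern holds in a limited form. As written, the sentence either conflicts with the document's own events (all participants) or lacks support (vaccinated women only). On the second reading the open quantity is 0 to 4 reported losses among vaccinated women: from 0/525 to 4/529 = 0.76% when only the losses are added back, and lower for a given number of losses if some of the 65 lost or withdrawn women were vaccinated.

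This rests on two assumptions: that pregnancy loss, perinatal death and hospitalization count as serious in the ordinary sense, since the document gives no definition; and that the position of the sentence after the 855 reflects the set it was based on. The documents do not show that any loss followed vaccination, and nothing here is evidence of harm from the vaccine. Effectiveness estimates for women and infants do not change. It should be corrected because it is a stated result that can mislead, not merely a missing detail.

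**What to change.** - State that the exclusions in Statistical analysis apply to the effectiveness analysis only.
- Base the safety statement on all enrolled women with known vaccination status, before exclusions, and give the denominators, including how many of the 65 lost or withdrawn women were vaccinated.
- Report the three spontaneous abortions and the perinatal death by vaccination status and by timing relative to vaccination.
- Replace the sentence with that count, or limit it to the population and event type that were actually assessed. In either case reconcile it with the hospitalization rows of Tables 2 and 3, and check the p-value of 0.277 in Table 3 at the same time.

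The cost is one short descriptive table from data the study should already hold, with no new model. The safety statement may become less favourable.

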77 during pregnancy (OR: 0.6; CI: 0.4-0.9).

78 ***Estimation of IVE in pregnant women***

79 Of the 855 pregnant women included in the analysis, 636 women were still pregnant  
80 during the 2019-2020 influenza season and comprised the study group for the  
81 estimation of IVE in pregnancy. Of them, 406 women (63.8%) were vaccinated  
82 against influenza and 230 (36.2%) refused vaccination. Table 1 shows their  
83 characteristics by influenza vaccination status.

84 Twelve of the 636 pregnant women tested positive for influenza (8 cases of influenza  
85 A/H3N2, 2 cases of A/H1N1 and 2 cases of influenza B). Table 2 summarizes their  
86 morbidity by influenza vaccination status. The incidence of influenza differed  
87 between vaccinated women (6/406; 1.47%) and unvaccinated women (6/230; 2.6%),  
88 however the difference was not statistically significant. Similarly, higher rates of  
89 febrile episode, ILI, pneumonia, healthcare seeking, hospitalization, use of antibiotics  
90 and antivirals were noted in the unvaccinated group compared to the vaccinated  
91 group, however none of these differences reached statistical significance (Table 2).  
92 The IVE of QIV against influenza was 43.5% for pregnant women during 2019-2020  
93 in Greece. The IVE of QIV against influenza was 43.5% (95% CI: 28.4%-55.6%) for  
94 pregnant women during 2019-2020 in Greece.

95 According to the regression model the age was not a predictor of influenza onset in  
96 the sample of pregnant women. Influenza vaccination of pregnant women reduced  
97 their logit to develop influenza by -4.2 (95% CI -3,7 -4,7), which indicates that  
98 influenza vaccination added a statistically significant protection to pregnant women.

99 ***Estimation of IVE in infants***

100 A total of 474 infants were born before or during the 2019-2020 influenza season and  
101 constituted the group for the estimation of IVE in infants. Their mean birth weight  
102 was 3189 g (range: 630-4650 g) and their mean gestational age was 39.1 weeks  
103 (range: 28-42 weeks). There were 281 (59.3%) infants whose mothers were  
104 vaccinated during pregnancy and 193 (40.7%) infants of unvaccinated mothers. The  
105 unvaccinated mothers had a mean gestational age of 31.2 weeks at enrollment  
106 compared to a mean gestational age of 28.3 weeks of vaccinated mothers (p-value

107 <0.001); no other significant difference was noted between the two groups (data not  
108 shown).

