109 Overall, 8 of the 474 infants tested positive for influenza (5 cases of influenza  
110 A/H3N2, 2 cases of influenza A/H1N1 and 1 of influenza B). Table 3 summarizes  
111 their morbidity by maternal influenza vaccination status. Infants of unvaccinated  
112 mothers more often developed influenza, febrile episodes, ILI, ARI, AOM and  
113 pneumonia and had increased rates of healthcare seeking, hospitalization, use of  
114 antibiotics and use of antiviral agents compared to infants whose mothers were  
115 vaccinated, however these differences reached statistical significance only for ARI  
116 and use of antiviral agents (p-values=0.012 and 0.036, respectively). The IVE against  
117 influenza for infants was estimated at 31.4% in 2019-2020. The IVE against influenza  
118 for infants was estimated at 31.4% (95% CI: 4%-51%) in 2019-2020.

119 According to the regression model the age of pregnant women was not a predictor of  
120 influenza onset in the sample of young infants. Additionally the influenza vaccination  
121 of pregnant women reduced the logit of their infants to develop influenza by -4.2  
122 (95% CI -3.6, -4.9), which indicates that influenza vaccination during pregnancy  
123 added a statistically significant protection to young infants.

124

125

126

127

128

129 **Table 1. Characteristics of pregnant women (n=636) by influenza vaccination status**130 **Characteristic** **Vaccinated** **Unvaccinated** **P-value**131 **n=406 (%)** **n=230 (%)**

132 \_\_\_\_\_

133 Mean age, years (range) 33.1 (21-45) 32.3 (18-45) 0.055

134 Mean gestational age, weeks (range) 19.3 (3-39) 21.6 (3-39) 0.003

135 Underlying disease 49 (12.2) 32 (14.0) 0.512

136 Influenza vaccination the past season 94 (23.2) 14 (6.1) <0.001

137 Mean no. of cohabitants (range) 1.7 (0-8) 1.8 (0-8) 0.147

138 Children <5 years 161 (39.8) 79 (34.5) 0.190

139 Mean no. of children <5 years (range) 0.5 (0-3) 0.4 (0-3) 0.325

140 No smoking during pregnancy 350 (93.1) 173 (84.0) 0.001

141 142 Smoking during pregnancy 26 (6.9) 33 (16.0)

143 \_\_\_\_\_

144

145

146

147

148

149

150

151 **Table 2. Morbidity (%) of pregnant women (n=636) by influenza vaccination status**

152	Type of morbidity	Vaccinated	Unvaccinated	P-value
153		n = 406 (%)	n = 230 (%)	
154	Influenza*	6 (1.5)	6 (2.6)	0.314
155	Febrile episode	17 (4.2)	13 (5.7)	0.402
156	ARI	115 (28.3)	50 (21.7)	0.069
157	ILI	11 (2.7)	11 (4.8)	0.169
158	Pneumonia	2 (0.5)	4 (1.7)	0.118

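### The confidence interval printed for gestational age (OR 0.998; 0.998 to 0.999) is narrower than 855 women can give per week or per day, so it cannot support the significance statement

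*SAP*

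**What the plan says.** The Statistical analysis section plans a logistic regression for factors associated with vaccination in 2019-2020 and sets the threshold: p-values "of 0.05 or less were considered statistically significant". The result stands in the opening part of Results: "influenza vaccination in 2019-2020: lower gestational age (OR: 0.998; CI: 0.998", with the upper limit at the start of the next line: "0.999), influenza vaccination the past season (OR: 8.8; CI: 4.7-16.2), and no smoking". No unit is given for the gestational-age odds ratio, and no confidence level or p-value for any of the three factors.

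The figures needed to check the interval are in the same document:

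- Sample and outcome split: "Of the 855 pregnant women, 525 (61.4%) were vaccinated against influenza and 330" not.
- Gestational age in all 855 women: the mean at "enrollment was 23.3 weeks (range: 3-39 weeks").
- Gestational age by group in the 636 women of Table 1: "Mean gestational age, weeks (range) 19.3 (3-39) 21.6 (3-39) 0.003".
- Mothers of the 474 infants (Estimation of IVE in infants): the "unvaccinated mothers had a mean gestational age of 31.2 weeks at enrollment", against 28.3 weeks in vaccinated mothers, p<0.001.

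Gestational age is in weeks wherever its unit is given.

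**The concern.** An odds ratio close to 1 with a tight interval is not odd in itself if the unit is small, and an estimate equal to its lower limit to three decimals can be rounding. The width is another matter. It is limited by the number of women and the spread of gestational age, and both can be bounded from the document. If the printed width is below that bound, the interval did not come from an ordinary 95% fit to these women on that scale, and it cannot be the evidence for a significance claim.

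Gestational age is one of only three factors declared significant, and it differs between the groups in both IVE cohorts. A reader who wants to judge this imbalance cannot recover its size, unit or precision from the printed result.

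**Working it through.** **1. Widest interval compatible with the print.** Limits of 0.998 and 0.999 to three decimals allow at most 0.9975 to 0.9995. The width is 0.0020, and the half-width on the log scale is (ln 0.9995 − ln 0.9975)/2 = 0.00100.

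**2. Largest possible SD.** With mean 23.3 and range 3 to 39 weeks, SD ≤ √[(39 − 23.3)(23.3 − 3)] = √(15.7 × 20.3) = 17.85 weeks. This would need every woman to be enrolled at week 3 or week 39.

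**3. Floor on the width.** For a maximum-likelihood logistic slope, SE ≥ 1/[SD × √(0.25 N)]. The 95% width on the OR scale is about 2 × 1.96 × SE × 0.998.

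- Per week: SE ≥ 1/(17.85 × √213.75) = 0.00383; width at least 0.0150.
- Per day: SE ≥ 0.00383/7 = 0.00055; width at least 0.00214.

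Both exceed 0.0020. If the mean and range are rounded generously (mean 23.25, range 2.5 to 39.99), the daily floor is still 0.00205. Covariates and missing records cannot lower the floor.

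**4. Realistic SD (an assumption, since no SD is printed).** Table 1's p=0.003 corresponds to t = 2.979, so SD = (2.3/2.979)/√(1/406 + 1/230) = 0.772/0.0825 = 9.35 weeks (8.8 to 9.9 allowing for rounding).

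For all 855 women it is somewhat larger. The 636 average (406 × 19.3 + 230 × 21.6)/636 = 20.1 weeks, so the other 219 must average (855 × 23.3 − 636 × 20.13)/219 = 32.5. If those 219 have an SD of 3 to 7 weeks (assumed), the overall SD is 9.8 to 10.3. This takes Table 1's gestational age to be the value at enrollment.

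**5. Expected interval at OR 0.998.** SE = 1/[SD × √(N p(1 − p))], with N p(1 − p) = 855 × (525/855) × (330/855) = 202.6.

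| SD, weeks | Unit | SE | 95% CI | Width | Width ÷ 0.0020 | p |
|---|---|---|---|---|---|---|
| 9.35 | week | 0.0075 | 0.983 to 1.013 | 0.0294 | 14.7 | 0.79 |
| 10 | week | 0.0070 | 0.984 to 1.012 | 0.0275 | 13.7 | 0.78 |
| 9.35 | day | 0.00107 | 0.9959 to 1.0001 | 0.0042 | 2.1 | 0.06 |
| 10 | day | 0.00100 | 0.9960 to 1.0000 | 0.0039 | 2.0 | 0.046 |

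Simulated logistic fits at N = 855 also gave a daily width of 0.0042. At SD 9.35, even the widest printed interval would need about 3,800 women on the day scale or 185,000 on the week scale. On the day scale, rounding of the OR alone (0.9975 to 0.9985) moves p from 0.02 to 0.16 at SD 9.35.

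**6. Is the confidence level the cause?** The rates of vaccination by past-season history, those with a history against those without, are given as "of vaccination (91.8% versus 55.1%, p-value<0.001"). They imply about 135/147 against 390/708, a crude OR of (135 × 318)/(12 × 390) = 9.2 (95% CI 5.0 to 16.9), with SE 0.311. The printed 8.8 (4.7 to 16.2), read as 95%, has SE ln(16.2/4.7)/3.92 = 0.316. That interval behaves as an ordinary 95% interval from these women. The gestational-age interval does not.

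**7. Point estimate against Table 1.** The slope implied by Table 1 is −2.3/9.35² = −0.0263 per week, an OR of about 0.974 (0.957 to 0.991), or 0.9962 (0.9938 to 0.9987) per day. This is unadjusted and in 636 women. On the log scale, 0.974 per week is about 13 times as far from 1 as 0.998 (0.0263 against 0.0020).

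**The case against.** The strongest reply accepts the width calculation and disputes what is built on it.

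- **A reader might infer that gestational age is not associated with vaccination.** The document does not support that. Its t-tests (p=0.003 in Table 1, p<0.001 among the infants' mothers) do not depend on the regression interval, and both point to lower gestational age in vaccinated women. This part of the reply stands in full.
- **A reader might infer that the odds ratio is non-significant once the interval is widened.** On the day scale this cannot be asserted: p is about 0.05 and changes sides with the SD and with rounding. On the week scale the p of about 0.8 keeps a point estimate that is itself in doubt. The value implied by Table 1, 0.974, has an interval that excludes 1, so a corrected weekly result may well be significant.
- **The gap between 0.998 and 0.974 need not be an error.** One figure comes from a regression that appears to cover all 855 women, the other from a crude comparison in 636. On the day scale, the Table 1 interval of 0.9938 to 0.9987 contains 0.998. The gap therefore calls for a check of the unit or the estimate and does not prove a wrong model.
- **The floor assumes a maximum-likelihood fit.** The Statistical analysis section also mentions Bayesian model selection with a random intercept, and it is unclear whether that covers this model. The caveat is limited: a random intercept would generally widen an interval, and the neighbouring odds ratio looks like an ordinary 95% result.
- **A reader might infer that the effectiveness estimate is affected.** It is not. The stated IVE formula is a ratio of incidence rates and does not use this odds ratio.

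None of this rescues the printed interval.

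**Conclusion.** The gestational-age interval cannot be right as printed on either scale. Against the widest reading of the print (0.0020), the width must be at least 0.015 per week or 0.0021 per day. This rests only on the stated N, mean and range and on an ordinary 95% fit. At an SD of about 9.4 to 10 weeks, which is derived and not stated, the interval is about 14 to 15 times too narrow per week or 2 times per day.

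The significance statement is therefore not supported by the interval offered for it. That is the limit of the finding: the association may be real, and whether the corrected odds ratio is significant is open. It is a minor reporting error in a secondary, descriptive analysis.

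**What to change.** Check the regression output, or refit if the output does not settle the matter. State the unit and the confidence level, and re-report the OR, CI and p-value with enough decimals to show the interval. Per week is preferable, as the unit used throughout. Keep the statement of significant association only if the corrected interval excludes 1. State as well which women the model includes and which covariates it adjusts for, so that the result can be compared with Table 1.

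The cost is one check or one refit and a corrected line in Results. The interval will become wider, and no effectiveness figure changes.
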